#### **7.3.13. Procedure Day 6: Lidocaine Patch 5% (Mylan)**

- A brief symptom-directed physical exam, if indicated.
- Vital signs to determine blood pressure, pulse, temperature, and respiratory rate.
- PSI assessment (as explained in **section 9.2.3.**) at patch application sites will be performed at the 24 and 39 hour time points.
  - Approximately 5 mL of blood will be drawn by an experienced nurse or phlebotomist in the CRU at:
    - 24:00 hours  $\pm$  30 minutes after patch application (vital signs obtained)
    - 27:00 hours  $\pm$  30 minutes after patch application
    - 30:00 hours  $\pm$  30 minutes after patch application
    - 33:00 hours  $\pm$  30 minutes after patch application
    - 36:00 hours  $\pm$  30 minutes after patch application
    - 39:00 hours  $\pm$  30 minutes after patch application (vital signs obtained)
- Subjects are free to leave the facility between these visits and at the end of the day, but must arrive at the facility in time for scheduled blood draw the following day.

#### **7.3.14. Procedure Day 7: Lidocaine Patch 5% (Mylan)**

- A brief symptom-directed physical exam, if indicated.
- Vital signs to determine blood pressure, pulse, temperature, and respiratory rate.
- PSI assessment (as explained in **section 9.2.3.**) at patch application sites will be performed.
- Approximately 5 mL of blood will be drawn by an experienced nurse or phlebotomist in the CRU at:
  - 48:00 hours  $\pm$  30 minutes after patch application (vital signs obtained)
- Subjects are free to leave the facility as this completes the study.
- A total of 18 blood draws will be completed over a period of 48 hours (total blood volume drawn = approximately 90 mL).

#### **7.4. Early Termination Visit**

An Early Termination Visit should be performed for any subject who discontinues their participation in the study prior to completing all procedure days. If a subject leaves the study before the last

procedure day, the subject will be asked about his/her reasons for termination. This may occur via telephone call or by email from a member of the study team. If the subject identifies one or more adverse events as their reason, then a brief physical exam should be performed. All withdrawals will be documented on a subject withdrawal form for study records.

### **7.5. Unscheduled Visit**

If an unscheduled visit occurs, a member of the study team will interview and evaluate the subject to determine the cause of the visit and provide care as needed and information documented on a supplemental visit form.

## 8. STUDY PROCEDURES/EVALUATIONS

### 8.1. Clinical Evaluations

Serum pregnancy tests will be performed at the screening visit before enrollment for all women of childbearing potential. Urine pregnancy tests will be performed on the morning of the first day of each of the three study arms if it has been more than 30 days since the subject's negative serum pregnancy test. If any test is positive, the subject will be excluded from further participation, counseled, and referred to a clinical facility.

On each of the procedure days, the subjects will be interviewed about any new, continuing, or worsening symptoms. Vital signs will be recorded before patch application or IV injection and at specified times in each procedure day (as indicated in **section 7.3.**). A CRU nurse or member of the study team will determine if the subject has any reportable symptoms. If appropriate, the MAI will be contacted and a symptom-directed physical exam will be completed. Results of the physical examinations and vital sign assessments will be reported to the ISM to determine if there is evidence of immediate safety concerns or for changes in values that indicate a potential danger to the subject should the subject continue in the study. After conclusion of each study arm and discharge from the CRU, subjects will be asked to report all adverse events (AE) for up to 48 hours. Subjects will be interviewed by telephone daily for two consecutive days (up to 48 hours) after the last procedure day of each study arm to determine if any AE occurred in the 48 hours post-discharge. If an event is judged to be a Serious Adverse Event (SAE), an SAE data collection form will be completed and SAE reporting procedures followed.

### 8.2. Laboratory Evaluations

#### 8.2.1. Clinical Laboratory Evaluations

In the event of an AE (of moderate severity or more) or SAE, safety laboratory data will be drawn, including hematology and chemistry parameters and provided to the MAI and ISM. Chemistry parameters include sodium, potassium, chloride, bicarbonate, BUN, creatinine, AST, ALT. Hematology parameters include Hgb, Hct, WBC and platelets. All tests are considered normal if the parameters are within normal limits or acceptable ranges, according to **Appendix B**.

#### 8.2.2. Bioanalytical Methods

Serum samples will be analyzed using validated quantitation methods, which will be developed and performed by [name], and his laboratory members at Long Island University. [name] group will meet conditions in the FDA guidance for Bioanalytical Method Validation 2012.

#### 8.2.3. Method for Determining Drug Content in Worn and Unworn Transdermal Systems

##### 8.2.3.1. Worn Systems

For the determination of residual content, the used patches will be sent to [name]' laboratory at Long Island University on the day after the patches are removed from the subject using expedited, temperature-controlled, next day delivery service. The appropriate extraction technique will be determined and developed by [name] group.

### **8.2.3.2. Unworn Systems**

A minimum of 10 unworn systems from the same lot number worn by the subjects will be analyzed for drug content.

The amount of drug absorbed will be calculated as follows:

Amount of drug absorbed=mean amount of drug in unworn systems – amount of drug in worn system

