	

• Patch studies: 60 min pre-application, during the 12 hour patch wear, and up to 48 hour post patch application

• 60 min pre-IV injection and then up to 10 hour post IV injection

 
B) Residual Drug Analysis Determination of Strength In conjunction with the above described pharmacokinetic study, residual drug analysis will also be conducted for the lidocaine patches.
 

• The worn patches are retained for drug content analysis.

• Upon removal of the product after prescribed wear period, the skin (at site of application) is swabbed and the swabs are retained for drug content analysis

--	---

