### 3. OBJECTIVES

#### 3.1. Study Objectives

The objectives of these studies are: 1) to determine the absolute bioavailability of lidocaine topical patches; 2) to determine the residual drug content in worn topical lidocaine patches; and 3) to apply mathematical models (e.g., deconvolution) to determine absorption rates from worn patches based on residual drug content and derived PK parameters.

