#### 3.2. Study Outcome Measures

The main outcome measure of the study is the determination of the pharmacokinetic parameters of lidocaine in healthy adult subjects; i.e., clearance (CL), volume of distribution (V), elimination rate constant ( $K_{el}$ ), maximum serum concentration ( $C_{max}$ ), time of maximum serum concentration ( $T_{max}$ ) of lidocaine and area under the serum concentration-time curve (AUC). In addition, we will determine residual drug content from worn lidocaine patches to estimate total amount of absorbed lidocaine.

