- If a patch has an adhesion score  $\geq 2$  at any time, a member of the study team may apply a small piece of medical tape to the corners of the patch in order to keep the patch in contact with the skin. Great care will be taken that the smallest area possible on the patch is covered by tape, so as not to alter drug absorption in any way.
- The patches will be removed at 12 hours. A PSI assessment will be recorded for each patch site.
- Upon removal, each patch will be placed back on its release liner (care will be taken to put the patch on the correct side of the release liner) and inserted into its original pouch. All three pouches will be placed together into a sealable foil pouch. Subject ID and date will be labeled on the outside of the foil pouch.
- The area of the skin where the patches were applied will be wiped with alcohol swabs (a different swab for each different patch site); the swabs will be numbered and placed into a second sealable foil pouch with the Subject ID and date.
- The day after removal, the patches will be shipped to Long Island University to be analyzed for residual drug content.
- Subjects are free to leave the facility but must arrive at the facility in time for scheduled blood draws the following day.

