## 10. PHARMACOKINETICS AND STATISTICAL CONSIDERATIONS

### 10.1. Study Hypotheses

The main objective of this study is to determine the absolute bioavailability and PK parameters (e.g., AUC,  $C_{max}$ ,  $T_{max}$ , CL, V) of lidocaine in healthy adults after using lidocaine 5% patches manufactured by Endo Pharmaceuticals and Mylan. The secondary objective is to determine residual drug content in worn patches.

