### 10.2. Pharmacokinetic (PK) Analyses

Lidocaine concentrations will be measured in serum samples collected from each subject. Blood samples (approximately 5 mL each) will be collected at the time points list in **section 4**. Actual sampling times will be used to estimate PK parameters.

Non compartmental and compartmental analyses will be conducted to estimate the primary PK parameters such as clearance (CL), volume of distribution (V), elimination rate constant ( $K_{el}$ ), maximum serum concentration ( $C_{max}$ ), time of maximum serum concentration ( $T_{max}$ ) and area under the serum concentration-time curve (AUC). Absolute bioavailability will be calculated as follows:

$$\text{Absolute bioavailability} = \frac{AUC_{patch}/Dose_{patch}}{AUC_{IV}/Dose_{IV}}$$

**Equation 1:** For determination of the absolute bioavailability for the Lidoderm® 5% patches (Endo Pharmaceuticals) and the lidocaine 5% patches (Mylan). The patch refers to the topical lidocaine patch systems. The geometric means for  $AUC_{0-\infty}$  will be obtained by exponentiating the log transformed  $AUC_{0-\infty}$  for the two treatments to determine the absolute bioavailability.

Different mathematical approaches including, but not limited to, deconvolution will then be utilized to determine secondary objectives and the rate of drug delivery from the patches. The secondary objective to determine residual drug content in worn patches would provide a surrogate method to determine the amount of drug delivered *in vivo* after wearing the patch. The following equation will be used to determine the amount of drug delivered *in vivo*:

$$\text{Lidocaine released} = \text{Total lidocaine} - \text{residual lidocaine}$$

**Equation 2:** The cumulative amount of lidocaine released by Lidoderm® 5% patches (Endo Pharmaceuticals) or lidocaine 5% patches (Mylan) at the end of the study arm will be obtained by subtracting residual lidocaine still remaining in the patch at the end of the study arm from the total amount of the drug present in an unused patch.

Further calculation will determine the rate of drug release from the patches using the following equation:

$$\text{Release rate} = \frac{\text{Lidocaine released}}{\text{Application duration}}$$

**Equation 3:** Determination of lidocaine release rate using the amount of lidocaine released from the patches.

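### The amount-absorbed formula (unworn minus worn patch) has no term for the per-site skin swabs, so lidocaine wiped off the skin is counted as absorbed

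*Combined protocol and SAP*

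**What the plan says.** Section 8.2.3.2 gives the rule: "Amount of drug absorbed=mean amount of drug in unworn systems – amount of drug in worn system". It has two terms, both patch contents.

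Other sections read the patch residual in the same way. Section 3.2 states that "we will determine residual drug content from worn lidocaine patches to estimate total amount of absorbed lidocaine". Section 10.2 introduces Equation 2 with "The following equation will be used to determine the amount of drug delivered" in vivo, although the equation itself calls its result lidocaine released and subtracts only what remains in the patch. Objective 3 in section 3.1 is to apply models "to determine absorption rates from worn patches based on residual drug content and derived PK parameters".

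The plan also collects the missing piece. In part B of the Protocol Summary, after patch removal, "the skin (at site of application) is swabbed and the swabs are retained for drug content analysis". Section 7.3.1 requires a different swab for each site, and "the swabs will be numbered and placed into a second sealable foil pouch with the Subject ID and date". Sections 7.3.5, 7.3.8 and 7.3.12 repeat this for the other patch periods.

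The swabs then drop out of the text. The shipping step reads "The day after removal, the patches will be shipped to Long Island University to be analyzed for residual drug content". Section 6.6 ships used patches, section 8.3.2 ships serum, section 8.2.3 describes content methods for worn and unworn systems only, and section 14.3 lists patch and serum drug levels without swabs.

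**The concern.** Drug that leaves a patch can enter the body or remain on the skin surface until it is wiped off. Unworn minus worn content measures the sum of the two. Lidocaine on an alcohol swab has been taken off the subject and cannot have been absorbed, but the section 8.2.3.2 rule counts it as absorbed. The swab amount cannot be negative, so the bias is always upward, and more subjects would not remove it.

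The absorbed amount is a small difference between two much larger contents, so a residue that is trivial against the patch content can be a large share of the result. The residue may also differ between a hydrogel patch and a polyisobutylene matrix patch, so the comparison of the two products on this measure could be distorted. The study offers residual analysis as a surrogate for drug delivered in vivo, to be set beside the pharmacokinetic estimate. An uncorrected upward bias in one of the two blurs that comparison.

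**Working it through.** **Inputs from the documents**

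- Lidoderm: 700 mg per patch (6.3.1); delivers 3 ± 2% over 12 hours; at least 95% (665 mg) expected to remain (6.1.1).
- Mylan: 140 mg per patch (6.3.3); delivers 11 ± 4% over 12 hours; at least 82% (115 mg) expected to remain (6.1.3).
- Three patches per application; 12-hour wear.
- Lidocaine on the swab: not given anywhere, so a range is assumed.

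**The plan's own figures**

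- Lidoderm residual: 0.95 × 700 = 665 mg, as stated.
- Mylan residual: 0.82 × 140 = 114.8 mg, stated as 115 mg.

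**Expected result of the section 8.2.3.2 formula, per patch**

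- Lidoderm: 0.03 × 700 = 21 mg.
- Mylan: 0.11 × 140 = 15.4 mg.

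This takes the stated delivery percentages as the loss from the patch. For Lidoderm that fits the stated floor: 3% + 2% = 5% lost leaves 95%. The Mylan floor of 82% does not follow from 11% + 4% in the same way (that would leave 85%), so it does not settle the reading.

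**Effect of a skin residue**

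Absorbed = formula result − residue. Overstatement = residue / (formula result − residue).

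| Residue, % of label | Lidoderm residue (mg) | Lidoderm absorbed (mg) | Overstated | Mylan residue (mg) | Mylan absorbed (mg) | Overstated |
|---|---|---|---|---|---|---|
| 0.25 | 1.75 | 19.25 | 9.1% | 0.35 | 15.05 | 2.3% |
| 0.5 | 3.5 | 17.5 | 20% | 0.7 | 14.7 | 4.8% |
| 1 | 7 | 14.0 | 50% | 1.4 | 14.0 | 10% |

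At 1% of label both products absorb 14.0 mg per patch, yet the formula reports 21.0 and 15.4 mg. Per subject (three patches) that is 63 mg against a true 42 mg for Lidoderm, and 46.2 mg against 42 mg for Mylan. Divided by 12 hours, the per-patch rates are 1.75 and 1.283 mg/h by the formula, against 1.167 mg/h for both.

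**Equal residue in mg**

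Scaling residue to label content gives Lidoderm five times Mylan's residue by construction (700/140 = 5). With 1.75 mg on the skin for both:

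- Lidoderm: 1.75 / 19.25 = 9.1%.
- Mylan: 1.75 / 13.65 = 12.8%.

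The overstatements are equal when the residues stand in the ratio 21 / 15.4 = 1.36. Lidoderm is affected more only if its residue in mg exceeds 1.36 times Mylan's, and the documents do not say.

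**The case against.** **The reach is limited.** Section 10.1 words the secondary objective narrowly: "The secondary objective is to determine residual drug content in worn patches". That is assayed directly, and a skin swab cannot bias it. For objective 3, no equation in section 10.2 computes an absorption rate from residual content: Equation 3 is a release rate, Equation 4 uses steady-state concentration and clearance, and deconvolution works on serum data. All of this is true. But section 3.2 says the residual is there to estimate absorbed drug, and objective 3 names residual content as a basis for absorption rates. Those uses take the biased quantity.

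**The size is assumed.** This stands. If the stated percentages are true delivery and not patch loss, the overstatement is residue divided by 21 or 15.4. Lidoderm then runs from 1.75/21 = 8.3% to 7/21 = 33%, and Mylan from 0.35/15.4 = 2.3% to 1.4/15.4 = 9.1%. The direction is the same under either reading.

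**The missing detail is only deferred.** The intent to assay the swabs is stated, section 8.2.3.1 also leaves patch extraction to the laboratory, and section 14.3 is a brief list that omits other data too. That weakens the point about methods. It does not help the formula, which is written out in full and leaves the swab term out.

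**Swabs are not the whole mass balance.** Worn patches go back onto their liners and into their pouches. Drug transferred there would also count as absorbed unless it is assayed. This is a fair addition and does not make the swab subtraction wrong.

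**Conclusion.** The concern holds. The section 8.2.3.2 rule, followed as written, reports drug released from the patch as drug absorbed, although the plan collects the material needed to separate the two. The upward direction is certain for any lidocaine on the swabs. The size cannot be fixed from the documents: under the assumed 0.25% to 1% of label it is 9% to 50% for Lidoderm and 2% to 10% for Mylan, and the order of the products reverses if equal amounts remain on the skin.

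The effect is confined to the residual-based estimate of absorbed drug and to any absorption rate built on it under objective 3. The log AUC and Cmax analyses in section 10.4 are untouched, and so is Equation 1 provided its patch dose, which section 10.2 does not define, means applied content. Equations 2 and 3 are sound under their own names; only the lead-in to Equation 2 is wrong. This should be corrected before the residual data are analysed.

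**What to change.** - **8.2.3.2:** define amount absorbed (delivered) = mean unworn content − content of the worn patch − lidocaine recovered on that site's swab, matched by patch number and summed over the three patches per subject.
- **3.2 and objective 3:** use this quantity wherever residual data stand for absorbed drug, and state which absorption-rate calculation, if any, takes it as input.
- **10.2:** keep Equations 2 and 3 as released drug and release rate, without the swab term. Change the lead-in to Equation 2 so that it refers to drug released from the patch.
- **7.3 and 8.2.3:** state that the swab pouch is shipped and assayed with the patches, give the extraction method, and report swab recovery. Say also whether liners and pouches are extracted with the patch.
- **14.3:** add swab drug content.

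The cost is a little more than wording. The swabs are already taken, numbered and kept, but a swab extraction and assay method has to be developed and its recovery shown. Swab assay error then enters the estimate, and incomplete recovery would leave part of the bias in place, which is why recovery must be reported. If the residue proves negligible, the data will show it.

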## **8.3. Specimen Preparation Handling and Shipping**

### **8.3.1. Instructions for Specimen Preparation, Handling, and Storage**

Blood samples will be collected during the procedures days at the time points specified in **section 4**. The CRU has a small well-equipped laboratory on site with a trained laboratory technician available to process the samples as required for this study, and the study coordinator/study team members will be available to assist with sample processing. The PI also has a well-equipped laboratory with appropriate equipment for sample processing. After processing, all samples will be stored in [name] lab at -80°C until shipped to Long Island University. During sample processing, the sera will be separated into two aliquots. One set of aliquots will be analyzed using an LC-MS validated method at Long Island University while the other set will be stored separately at the UI College of Pharmacy as a back-up set of samples.

### **8.3.2. Specimen Shipment**

Serum samples will be shipped to Long Island University for analysis using expedited temperature-controlled, next-day delivery service.

## 9. ASSESSMENT OF SAFETY

### 9.1. Specification of Safety Parameters

Assessment of AEs throughout each of the procedure days will be monitored and vital signs (blood pressure, temperature, pulse, and respiratory rate) for each subject will be periodically monitored. AEs at the patch application site (e.g., erythema, edema, itching) will be assessed subjectively by each subject and also examined by a member of the study team at study visits following patch removal. Subjects will be interviewed by telephone daily for two consecutive days (up to 48 hours) after completing each study arm to determine if any AEs occurred in the 48 hours following study arm completion. If any skin changes are noted by the subject, (s)he will be instructed to return to the CRU for evaluation. If any skin changes are seen on exam they will be defined as topical AEs. In addition, the MAI will be available to assess and treat (where indicated). When medically indicated, the subject will be admitted to UIHC for emergency and/or continued care. All adverse effects will be reviewed by the ISM, and all SAEs will be immediately reported to the IRB.

The administration of lidocaine is not anticipated to cause clinical problems. If a clinical problem would occur the subject will be discontinued from the study. If AEs occur, clinical judgment will be used with the results recorded as part of the PI or MAI's judgment of the probability that an event is linked to the procedure. Subjects will be followed until all AEs are resolved or until they become medically stable.

### 9.2. Methods and Timing for Assessing, Recording, and Analyzing Safety Parameters

#### 9.2.1. Adverse Events

AEs are qualified by expectedness, grade of severity, relationship of causality, and as serious or non-serious based on the definitions provided (**Appendices B and C**). All events will be recorded on appropriate clinical report forms with notation of duration, severity, and outcome. The PI is responsible for recording all AEs that are observed or reported during the study, regardless of their relationship to investigational product or their clinical significance.

##### 9.2.1.1. Adverse Event Definition

Any untoward medical occurrence in a subject administered a study product, which does not necessarily have a causal relationship with this procedure. An AE is defined as any noxious, pathologic, or unintended change in anatomic, physiologic, or metabolic functions, as indicated by physical signs, symptoms, and/or laboratory changes occurring in any phase of the clinical study, regardless of their relationship to study product. The occurrence of an AE may come to the attention of study personnel during study visits or interviews of a subject presenting for medical care, or upon review by a study monitor. AEs include:

- An exacerbation of a pre-existing condition
- A concurrent illness
- Any drug interaction
- Any event related to a concomitant medication

An AE can be any unfavorable and unintended sign (including an abnormal finding), symptom or disease temporarily associated with the use of a study product, whether or not related to the study product. This includes any occurrence that is new in onset or aggravated

in severity or frequency from the baseline condition, abnormal results of diagnostic procedures (including laboratory test abnormalities) which are considered AEs if they:

- Result in discontinuation from the study
- Require treatment or any other therapeutic intervention
- Require further diagnostic evaluation (excluding a repetition of the same procedure to confirm the abnormality)
- Are associated with clinical signs or symptoms judged by the investigator to have a significant clinical impact

All AEs including local and systemic reactions not meeting the criteria for “serious adverse events” should be captured on the appropriate case report form (CRF). Information to be collected includes event description, time of onset, assessment of severity, relationship to study product (assessed only by the PI or MAI), and time of resolution/stabilization of the event. All AEs occurring during the study must be documented appropriately regardless of relationship. All AEs will be followed until the subject becomes medically stable. Elective hospitalizations for pre-study conditions (e.g., elective cosmetic procedures) are not AEs.

